Reminders: A reminder call will be placed the day prior to participants' scheduled in-lab assessment. Research staff will mail a reminder to participants one week prior to their follow-up appointment.

2a.3.g. Data Collection Procedures. Recruitment will target Veterans with AUD and co-occurring PTSD in the outpatient SUD treatment at PAVAHCS (see section **2a.3.c.)**. To insure against acute alcohol intoxication, participants will be required to provide a Breath Alcohol Concentration (BrAC) of .00 prior to the beginning of each study visit. Should participants exceed this cut-off, they will be rescheduled for the following business day. Research staff will be trained on manualized assessment procedures and regularly observed by [name] (supervised by Drs. [name] and [name]) and regular meetings will be held to discuss testing and scoring questions. Inter-rater reliability will be determined with regularity throughout data collection. Staff administering the neuropsychological batteries will be blinded to participant condition.

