During the screening assessment, participants will provide written informed consent. Next, a more detailed assessment of inclusionary/exclusionary criteria will be conducted (see section 2a.3e. Measures) and participants will be compensated \$30 for completion of this screening assessment. Individuals not meeting inclusionary criteria will be excluded from the remainder of the study. Individuals meeting all criteria will be scheduled to return for a baseline assessment. More specifically, participants will be administered structured clinical interviews, self-report questionnaires and remaining neuropsychological assessments, to collect baseline levels of responding. Participants completing the baseline assessment will be compensated \$50. Participants will be randomized in a 1:1 ratio to condition (training or control) and a checklist will be used to ensure that all study criteria are met before randomizing a participant. Participants will return to the lab the next business day for orientation to cognitive training (or computer game control) procedures and will be issued a loaned computing device (for descriptions of training schedule and platform delivery see section 2a.3.h. Method Overview). Participants will be compensated 10\$ for completion of the orientation session. Over the course of 6-weeks, participants will complete 30 hours of home-based cognitive training or computer games at the rate of 5 hours a week. Participants will earn \$5 for each completed training session (up to \$25 a week; \$150 total). Participants will be asked to refrain from alcohol or other substance use at least 4 hours prior to and during completion of training exercises. They will be advised that it is best to work on the programs in a quiet, preferably private location. Participants will log-in to a web-based cognitive training program or gaming site using a number assigned to their loaned wireless equipped computing device. Participant's engagement (i.e., adherence) and performance data will be sent to a secure server (i.e., no participant identifiers or personal health information); the data uploaded on the server will be identified only by the participant's assigned device number. A de-identifier sheet linking the device number to participant will be locked in the lab with access limited to study staff (See "Human Subjects" for specific details regarding the data security protocol). Participants will return to the lab at the end of each training week (i.e., 5 visits) to complete selfreport measures and participate in check-ins with the study coordinator regarding their level of engagement in the protocol. Participants will be compensated \$10 each study week they complete their lab-based session.

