Depression and Anxiety: General levels of depression and anxiety will be measured at baseline and each study week with the 64-item Inventory of Depression and Anxiety Symptoms (IDAS; Watson et al., 2007).

Table 2. Overview of assessments to be administered

Clinical Assessments and Procedures	Phone Screen	Screening Visit	Baseline Assessment	Each Study Week	Week 3	Week 6 Post- Training	3 or 6 Month Follow up
Inclusion/Exclusion							_
Study Explanation	Χ						
Demographic Information	Х	Χ					
SCID-I – AUD		Χ					
CAPS – PTSD Interview		Χ					
Cognitive Screening-Table 1*		Х					
WTAR – Premorbid IQ Proxy		Х					
MMSE – Dementia Screen		Х					
DoD Severe TBI Screen		Χ					
Outcomes							
(S1) Acceptability/Usability Measures and Testing			X (orientation)		Х	X	
(S1) Interviews and/or Moderated Focus Groups					X	X	
Neuropsych Assessment			X			Χ	Χ
TLFB – Alcohol Consumption			X	Χ		Χ	X
DUQLS; IPF - Functional			X			Χ	X
PCL – M – PTSD symptoms			X	Χ		Χ	X
Potential Covariates, Second	lary Meas	ures					
TLFB - non-alcohol sub use				Χ		Χ	Χ
SCID-I (Axis 1 disorders)			X				
CAADID – ADHD			X				
AUDIT – AUD Severity			X	Χ		Χ	X
Training Adherence				Χ			
IDAS – Depression/Anxiety			X	Χ		Χ	Χ
PTI - Past/Current Treatment	Χ		X	Χ		Χ	X
Prescription Medication	Χ		X	Χ		Χ	Χ
Other							
Collateral h	istory fron	n medical re	cord/outpatien	t SUD tr	eatmen	t team as r	necessary
Study Informed Consent		Χ					
Randomization Checklist			Х				
Training Check-in Meetings				Х			
Breath Alcohol Concentration		X	Χ	Х		Χ	Χ

2a.3.j. Planned Data Analysis.

Missing Data. All laboratory-based measures will be reviewed for completeness immediately following collection, prior to the participant's dismissal. Despite our intensive protocol to limit participant attrition, we do expect missing data over the course of this study (i.e., 30%) and have adjusted our recruiting sample accordingly. To minimize the impact of missing data from incomplete protocols, we will use model-based multiple imputation procedures appropriate for longitudinal research described by Schafer and Graham (2002) and conduct analyses to evaluate the sensitivity of the results to model assumptions (Little & Rubin, 1987).

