The normality and range of data distributions will be examined and appropriate data transformations will be made when necessary. The data will also be screened for violations of assumptions underlying the statistical tests described below and when necessary, models will appropriately account for factors that vary with time across the study (i.e., training adherence). To control for Type-1 error rates cognitive outcomes will be tested using a Global Cognition Score (see 2a.3.i. Measures). Through randomization, we anticipate that the groups will be comparable in terms of demographic characteristics, premorbid intelligence, cognitive impairment, Axis-1 disorders, treatment participation, prescription medication use, training adherence and AUD and PTSD symptom severity. If significant differences exist, as indicated by Chi Square and t-tests, we will statistically adjust for these effects via inclusion as covariates in the analyses. We will conduct both a per protocol analysis on subjects who complete a minimum of 30 hours of training, and an intent-to-treat analysis on all randomized subjects, and report any differences in retention rates between the two conditions. For all models, variation inflation factors and tolerance will be obtained to assess for collinearity concerns. To account for family wise error, alpha will be adjusted in all secondary and exploratory analyses.

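### Randomisation is placed before the next-business-day orientation visit, so a participant who misses orientation is a randomised never-starter; randomising at the start of orientation would avoid this cheaply

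*Combined protocol and SAP*

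**What the plan says.** Section 2a.3.g gives the sequence in prose: screening visit, baseline assessment and its payment, then "Participants will be randomized in a 1:1 ratio to condition", with a checklist confirming that all criteria are met first. The text continues: "Participants will return to the lab the next business day for orientation to cognitive training (or computer game control) procedures". At that visit participants "will be issued a loaned computing device". They are paid $10 for completing orientation.

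The same section requires a breath alcohol concentration (BrAC) of .00 before each study visit. "Should participants exceed this cut-off, they will be rescheduled for the following business day".

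Table 2 lists a "Randomization Checklist", which appears to be marked in the Baseline Assessment column. The table has no orientation column.

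Section 2a.3.j plans a per-protocol analysis of subjects with at least 30 hours of training and "an intent-to-treat analysis on all randomized subjects". I found no rule for a person who is randomised but does not attend orientation: no replacement, no modified analysis set and no expected rate.

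**The concern.** The first arm-specific step that the plan describes is orientation. Allocating a visit earlier has no stated purpose, and it opens a gap in which a participant can be randomised and then receive neither program. The gap is normally one business day, but a failed BrAC check extends it. Recruits are newly enrolled outpatients who need not have detoxified before treatment entry (2a.3.b, 2a.3.c). The plan itself expects 30% attrition.

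What is at stake depends on what happens to never-starters afterwards:

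- If they are measured at 6 months, those in the training arm contribute an outcome without any training and pull the intent-to-treat difference toward zero.
- If they are lost, they use attrition allowance before treatment begins, and they are mixed into the between-arm retention comparison promised in 2a.3.j.
- If their outcomes are imputed from assigned arm without regard to adherence, they are credited with a benefit they could not have had.

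The power calculation allows for attrition. It makes no allowance for people who are measured but untreated.

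**Working it through.** **Inputs (2a.3.j, Power Analysis).** Two-sided independent-samples t-test, alpha .05, d = .60, 128 recruited for Stage 2 (64 per arm), 30% attrition, 90 analysed (45 per arm), stated power 80%.

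**Reproducing the plan's figure.**

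- Noncentrality = d / √(1/45 + 1/45) = .60 × √22.5 = .60 × 4.743 = 2.846, with 88 degrees of freedom. Power from the noncentral t distribution is 80.4%, which agrees with the stated 80%.
- Attrition: 128 × .70 = 89.6, about 90. Working back, 90 / .70 = 128.6, so 129 against the stated 128. This agrees.

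**Case A: never-starters are measured at 6 months.** Let f be the share of the analysed training arm that never started. It is an assumption; the documents give no value. Never-starters are taken to gain nothing from training. Those in the control arm do not change the contrast, because 2a.3.h does not expect the games to affect cognition. The expected difference is then d × (1 − f), put into the same formula with 45 per arm:

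| f | d × (1 − f) | Power | Analysed N for 80% | Recruits at 30% attrition |
|---|---|---|---|---|
| 0 | .600 | 80.4% | 90 | 129 |
| 1% | .594 | 79.6% | 92 | 132 |
| 2% | .588 | 78.8% | 94 | 135 |
| 5% | .570 | 76.2% | 100 | 143 |
| 10% | .540 | 71.7% | 110 | 158 |
| 20% | .480 | 61.5% | 140 | 200 |

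The last column is analysed N / .70, rounded up. Allowing for the extra variance from mixing starters and never-starters changes little: 75.9% at f = 5% and 71.0% at f = 10%.

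**Case B: never-starters are lost, within the 30%.** The analysed set is still 90, the effect among those observed is still .60, and power is still 80.4%. What changes is where the allowance goes. If 5% of those randomised never start, that is .05 × 128 = 6.4 people out of an allowance of .30 × 128 = 38.4, or one sixth of it, gone before anyone is treated.

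**Case C: never-starters are lost on top of the 30%.** Retained per arm = 64 × .70 × (1 − f), rounded:

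- f = 5%: 43 per arm, N = 86, power 78.5%
- f = 10%: 40 per arm, N = 80, power 75.5%
- f = 20%: 36 per arm, N = 72, power 70.9%

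This is lost sample size. The effect is not diluted.

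**How firm the timing is.** The sentence order in 2a.3.g puts randomisation between the baseline assessment and the return visit. No sentence says outright that it happens at the baseline visit. Table 2 is weak support, because its Baseline column also carries an entry labelled as orientation, so that column may cover both sessions. Figure 2, which might settle the order, is not reproduced in the text available.

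**The case against.** The strongest reply is that the exposure is small and already managed. The gap is one business day. Participants have by then attended two study visits under the same BrAC rule. A typical patient attends the treatment program about four days a week, and study staff are on the same grounds (2a.3.b). A positive BrAC leads to rescheduling and does not remove the participant. The plan has a locator form with two extra contacts, reminder calls before in-lab assessments, payment for orientation, multiple imputation with sensitivity analyses, a per-protocol analysis and reporting of retention by arm. Stage 1 tracks attrition and adherence before Stage 2 starts. Knowing the arm a day ahead may also help staff prepare different platforms and, in Stage 1, the usability laboratory session for training participants, although the documents do not give this as a reason.

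Most of this stands. It makes a low never-start rate plausible, and at 1% to 2% the cost in Case A is under two power points. It does not remove the structural point: no rule covers a randomised participant who misses orientation, and nothing described requires allocation before then.

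A reader might infer two stronger things that the documents do not support:

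- **That the intent-to-treat effect is necessarily diluted.** Dilution needs never-starters to be measured, or imputed without benefit. Someone who does not return may well be lost, and Case B then applies.
- **That staff knowing the arm a day early biases the trial.** Baseline measures are complete by then, neuropsychological testers are blinded to condition (2a.3.g), and the documents do not say when or to whom the allocation is disclosed.

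**Conclusion.** The point holds as an inexpensive improvement to sequencing. As 2a.3.g reads, a participant who misses orientation has been randomised, belongs in the intent-to-treat set and has received nothing.

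The size cannot be fixed from the documents. It ranges from no loss against plan (lost within the allowance) to about 2, 4 or 9 power points when 2%, 5% or 10% of the measured training arm never started. Those figures assume zero benefit in never-starters and complete 6-month measurement of them, which is the unfavourable case.

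The intent-to-treat test remains valid throughout. What is affected is its efficiency and how the estimate and the retention figures are read. The conclusion also rests on taking the sentence order in 2a.3.g as the real order; if randomisation already takes place at orientation, only the wording needs correcting.

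**What to change.** - **Section 2a.3.g:** state that randomisation and its checklist take place at the start of the orientation visit, after the participant has returned, met the existing BrAC requirement and been confirmed eligible, and just before the device is issued.
- **Table 2:** add an orientation column, or a footnote, so that the checklist is tied to that visit.
- **Participant flow:** count those who do not return as pre-randomisation losses, who can be replaced.

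The visits, staff and assessments stay the same. There are two costs. Both set-ups must be ready at each orientation. Replacing no-shows also takes some recruitment. If 5% did not return, randomising 128 would need 128 / .95 = 134.7, so 135 eligible people, which is 7 more. At the planned yield of 148 eligible from 222 screened, that is 7 / (148/222) = 10.5, about 11 more screened. At the goal of four eligible participants a month (2a.3.k), it is 7 / 4 = 1.75 months. At 2% the figures are 3 more eligible, about 5 more screened and .75 of a month. If no-shows are not replaced, the number randomised falls by the same small amount.

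The change does not remove people who collect a device and never log in, since training is done at home. For them, the plan should report never-starters by arm and say how the intent-to-treat analysis and the imputation treat them.

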Basic Attention and	Trail Making Test Part A*	Visuomotor Attention and Processing
Cognitive Bias	WAIS-IV Symbol Search	Speed
	WAIS-IV Digit Symbol	
	Approach-Avoidance Task	Attentional and Cognitive Biases

Verbal and Visual	Brief Visual Memory Test-R	Visuospatial learning and recall memory
Learning & Memory	Hopkins Verbal Learning Test–R*	Auditory learning and recall memory
Working Memory	WAIS-IV Arithmetic	Abstract Reasoning, Mental Calculation
	WAIV-IV Digit Span	Mental Tracking, Organization, Sequencing
	WAIS-IV Letter Numb Sequencing*	Mental Reorganization; Sequencing
Impulsivity and	Delis-Kaplan Color-Word Stroop Test	Inhibition of an over-learned response
Decision Making	Continuous Performance Task*	Sustained Attention, Vigilance, Inhibition
	Iowa Gambling Task	Decision-Making, Risk-taking
	Delay Discounting Task	Decision-Making, Reward Processing
Mental Flexibility	Wisconsin Card Sorting Task	Rule-Learning, Set-Shifting
	Delis-Kaplan Tower Task	Planning, Rule-Learning
	Trail Making Test Part B*	Speeded Set-Shifting

Measures: Alcohol Use

Alcohol Use. The Time-Line Follow-Back (TLFB) interview provides a calendar-guide of a targeted time period to help participants retrospectively record the number of standard drinks consumed on each day. The TLFB procedure has demonstrated good reliability and validity in past work across diverse samples (Sobell & Sobell, 1992) and data will be used to calculate the primary drinking outcome variable, average drinks per drinking day (the number of drinks consumed divided by the number of drinking days). The TLFB will be administered in an interview format at each study visit.

Breath Alcohol Concentration (BrAC). The *Intoximeter Alco-Sensor IV* (Intoximeters Inc.) instrument will be used to measure BrAC at each visit to ensure that subjects are not acutely intoxicated.

Measures: Functional Status and PTSD Symptom Severity.

Drug User Quality of Life Scale (DUQLS; Brogly et al., 2003). The DUQLS is a culturally relevant tool for assessing quality of life and satisfaction among individuals with SUD. Participants are also asked to classify each of the 22 life areas (including SUD treatment) as "important" or "unimportant" to them. Reponses on the DUQLS can be summed to generate an overall quality of life score as well as sub-scores that reflect quality of life in life areas that are important and unimportant to the participant.

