Stage 2, Aim 2 Hypotheses 1a - b. Participants who receive cognitive training as compared to those receiving a computer-game control training, will demonstrate at 6 month post-training follow-up: Aim 2 Hypothesis a (Primary): greater improvements in cognitive outcomes (Global Cognition Score); Hypothesis b (Secondary): reduced alcohol consumption (drinks per drinking day) and PTSD symptoms (PCL-M) and improved quality of life outcomes (DUQLS, IPF). In order to test these hypotheses, a series of 5 multiple linear regression tests will be conducted to assess the effect of condition on each primary outcome. Step 1 will include the baseline level of the primary outcome. Condition (intervention, control) will be entered on Step 2. Step 3 will include any necessary covariates (described above in *Planned Data Analyses*) to determine if effects still remain. From this model we will be able to estimate the covariate and baseline adjusted mean changes, and 95%CIs, in global cognition, alcohol use, PTSD and quality of life outcomes 6 months posttraining. Secondary analyses. Planned secondary analyses will mirror the above description for primary analyses. First, to follow-up the analysis with global cognitive functioning, we will explore the effects of cognitive training on targeted cognitive domains using individual Cognitive Domain Scores as outcomes. Second, although we expect gains observed in the cognitive training group to be sustained throughout the follow-up period (i.e., persistence of neuroplasticity based cognitive training benefits), we will determine whether the Global Cognition Score changed from post-training to follow-up. This statistical approach is more dismantled and therefore more specific, and offers several advantages over repeated measures ANCOVA.

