Stage 2, Aim 2a Exploratory Hypothesis. Changes in global cognition will be significantly associated with decreases in alcohol consumption, PTSD symptom severity and increases in quality of life outcomes. Change scores will be computed for the Global Cognition Score, average drinks per drinking day, the PCL-M and the DUQLS and IPF, by computing the difference between follow-up and baseline. Four Pearson correlations will be performed to test associations between composite index change scores for Global Cognition and the 4 recovery outcomes. Exploratory Mediation and Moderation. We will explore potential mediators (i.e., training adherence and performance) and moderators (i.e., AUD and PTSD severity; Alcohol Use) of the effects of training condition on cognitive outcomes. The MacArthur approach to moderation and mediation analysis (Kraemer et al., 2008) will be employed. These analyses are considered exploratory

because, although the study is powered to detect main effects, we will have power to detect only very strong interaction and mediating effects.

2a.3.k. Timeline for Primary and Secondary Research Activities (See Table 3).

Primary Research Activities. During the start-up phase (months 1-3) of the proposed work, we will coordinate recruitment procedures with the outpatient SUD treatment program, finalize and purchase assessment and training tools and train study personal in the study protocol. A recruitment goal of 4 eligible participants per month was chosen based on prior experiences of the mentorship team who agreed that the goal was realistic and sufficient to meet study objectives, and to allow adequate time to conduct follow-up assessments. Recruitment for Stage 1 will start month 4 and last for 5 months. The weekly and post-training assessments for Stage 1 will be completed in month 9 and 3 month follow-ups will be completed in month 12. We will reserve time during months 13 and 14 to incorporate feedback from Stage 1 to refine the protocol and optimize feasibility for Stage 2. Stage 2 recruitment will begin at month 15 and will last until approximately month 46-47. Therefore, including start-up and Stage 1, all data should be collected by the *middle of year 5*.

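### Drinks per drinking day, the only alcohol measure tested under secondary Hypothesis b, is 0/0 for a participant with no drinking days, and the plan states neither a value for that case nor the TLFB window

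*Combined protocol and SAP*

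**What the plan says.** **Outcome.** Section 2a.3.i (Measures: Alcohol Use) defines the drinking outcome as "average drinks per drinking day (the number of drinks consumed divided by the number of drinking days". The source is the TLFB interview, which "provides a calendar-guide of a targeted time period to help participants retrospectively record the number of standard drinks consumed on each day". On timing it says "The TLFB will be administered in an interview format at each study visit". Table 2 also gives only the visits at which the interview takes place.

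**Use.** In section 2a.3.j, Hypothesis b (labelled secondary) predicts "reduced alcohol consumption (drinks per drinking day) and PTSD symptoms (PCL-M) and improved quality of life outcomes (DUQLS, IPF". Drinks per drinking day is the only alcohol measure in it. AUDIT is collected, but it is listed among potential covariates and secondary measures. Each outcome is tested by linear regression, where "Step 1 will include the baseline level of the primary outcome" and condition follows at Step 2. The exploratory hypothesis needs the ratio at both times: "Change scores will be computed for the Global Cognition Score, average drinks per drinking day, the PCL-M and the DUQLS and IPF".

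**Rules that might apply.** Section 2a.3.j plans "an intent-to-treat analysis on all randomized subjects" alongside a per-protocol analysis. It plans multiple imputation for data missing because a protocol was incomplete. On distributions it says "The normality and range of data distributions will be examined and appropriate data transformations will be made when necessary".

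No section gives a value, an exclusion rule or another model for a participant with no drinking days, and none gives the look-back length at baseline or at six months.

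**The concern.** In a trial run inside alcohol treatment, a window with no drinking is the best alcohol result, and it is the one result that the formula cannot score. A regression has no outcome value for such a participant and omits the record unless told otherwise. The arms are then compared only among people who drank after randomisation, which is not a randomised comparison, and a benefit that works through abstinence is not counted.

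Because the rule is unwritten, it could be chosen after the data are seen. The missing window adds to this: it decides how often 0/0 occurs, since the longer the window, the fewer participants have no drinking day in it.

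**Working it through.** **1. Is the case covered elsewhere?**
- *Imputation.* The Missing Data paragraph concerns incomplete protocols. A completed TLFB that shows no drinking is complete, so the rule does not reach it. Imputing would also assign drinking to people known not to have drunk.
- *Transformation.* A transformation acts on values that exist. It cannot give 0/0 a value.
- *Intent-to-treat.* This requires a result for every randomised participant, which the formula does not supply.
- *Interview at each visit.* This could be taken to mean since the last visit, but the text does not say so. Table 2 places the first alcohol TLFB at baseline, so that reading would leave the baseline window open.

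**2. Can it occur?** Section 2a.3.a describes treatment-seeking participants in early recovery, so a window without drinking is realistic. Section 2a.1 stresses the risk of relapse, and a since-last-visit window at follow-up could approach six months; both make it less common. At baseline it is less likely, because current AUD is required (2a.3.e) and detoxification before entry is not (2a.3.b). The documents give no rate.

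**3. Does the rule change the estimate?** Let *p* be the proportion abstinent and *m* the mean among drinkers.
- Abstainers dropped: difference = m(training) - m(control).
- Abstainers scored 0: difference = (1 - p)m for training minus (1 - p)m for control.

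All rates and means below are assumptions.

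| Abstinent, control v training | Drinkers' mean, both arms | Dropped | Scored 0 |
|---|---|---|---|
| 30% v 50% | 8 | 8 - 8 = 0.0 | 4.0 - 5.6 = -1.6 |
| 10% v 20% | 8 | 8 - 8 = 0.0 | 6.4 - 7.2 = -0.8 |

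**4. Selection among drinkers.** The 0.0 assumes that abstinence is unrelated to drinking level. A simulation used 45 per arm, 30% v 50% abstinent, no training effect on anyone's drinking level, and abstainers taken as exactly the least or exactly the most severe, with severity correlated up to .5 with drinking level. The drinkers-only estimate ran from -0.4 to +0.5 drinks. The sign depended on who abstained.

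**5. Equal abstinence.** If *p* is the same in both arms and training changes drinking among drinkers by *D*, dropping abstainers estimates D and scoring 0 estimates (1 - p)D. With p = 0.30 and D = -2.0, these are -2.0 and 0.70 × (-2.0) = -1.4. So the two rules agree under equal abstinence only when D = 0.

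A simulation with 45 per arm, 30% abstinent in both arms, a nominal effect of -2.4 drinks (0.6 of an assumed SD of 4) and a floor of 1 drink gave about -2.2 for drinkers only and about -1.5 with zeros. The chance of a significant benefit at .05 was about 75% and 39%.

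**6. The plan's power figure.** With 45 per arm, d = .60 and two-sided alpha .05, a t-test has 80.4% power, so the stated 80% reproduces. That d is the plan's cognitive effect size. For alcohol the plan cites partial η² of .10 to .16. Read as a two-group contrast (an assumption), d = 2√(η²/(1 - η²)) = 0.67 to 0.87. If 20% of 90 were dropped, power at .05 would be 80 to 96%; if 50% were dropped, 59 to 82%.

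**The case against.** The best defence is that only one reading fits the written rules. Dropping abstainers conflicts with intent-to-treat, imputation is confined to incomplete protocols, and a zero is the natural score, so what is missing is an unwritten convention. Much of this stands: imputation is not a reading that the documents leave open. But the zero is not written, regression software drops an undefined value by default, and the window would still be missing.

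A second defence is that scoring 0 has a cost. Drinks per drinking day measures intensity, and an effect confined to intensity is diluted by zeros. This stands in full, and the example with 30% abstinent in both arms shows its size. A case made only from scenarios with no effect among drinkers would be one-sided.

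Third, the frequency is unknown and the outcome is secondary. Both are true, and they limit the weight of the point.

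A reader might infer more than the documents support:
- *That the trial's main result or sample size is at risk.* Section 2a.3.i calls this the primary drinking outcome, and the analysis text speaks of each primary outcome. But Hypothesis b is labelled secondary, and the sample size rests on the cognitive hypothesis.
- *That power falls from 80% to 50% when half the sample is dropped.* That applies the cognitive d of .60 to an alcohol outcome for which the plan cites larger effects.
- *That the outcome must be replaced by drinks per day.* That changes the construct and is not needed to resolve 0/0.

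**Conclusion.** The point holds and should be fixed. The ratio is undefined for participants with no drinking days, no rule in the documents covers them, and the TLFB window is not stated. Applied as written, the analysis drops them, against the plan's own intent-to-treat commitment.

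The omission is certain from the text. Its size is not, because the abstinence rates, the 8-drink mean and the effects among drinkers are all assumed. Under those assumptions the choice of rule moves the estimate by 0.8 to 1.6 drinks when abstinence differs between arms with no effect among drinkers, and from about -2.2 to -1.5 when 30% abstain in both arms and training lowers intensity. Neither rule always favours training. The reach is one of four secondary outcomes and one exploratory correlation.

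**What to change.** Before any outcome data are seen, add to 2a.3.i and 2a.3.j:

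1. The TLFB window used for the outcome at baseline and at follow-up.
2. A completed TLFB with no drinking days is scored 0 at both times and treated as observed, not imputed.
3. Confidence intervals for this outcome are robust or bootstrap, because a transformation will not remove a cluster of zeros.
4. Drinks per drinking day among drinkers is reported as a supporting comparison, labelled as not randomised.

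This is wording only: the TLFB already records drinks for each day, and the chosen outcome is kept. The cost is the dilution shown in the working, a smaller estimate and less power if training lowers intensity without changing abstinence. Item 4 keeps that effect visible. Testing drinks per day instead is optional.
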